**(b) Significance:** In this proposal, we extend our previous SPIRE feasibility and preliminary effectiveness study to examine STEP-Home efficacy in a RCT design. This novel therapy will target the specific needs of a broad range of underserved post-9/11 Veterans. It is designed to foster reintegration by facilitating meaningful improvement in the functional skills most central to community participation: emotional regulation (ER), problem solving (PS), and attention functioning (AT). The skills trained in the STEP-Home workshop are novel in their collective use and have not been systematically applied to a Veteran population prior to our SPIRE study. STEP-Home will equip Veterans with skills to improve daily function, reduce anger and irritability, and assist reintegration to civilian life through return to work, family, and community, while simultaneously providing psychoeducation to promote future engagement in VA care.

The innovative nature of the STEP-Home intervention is founded in the fact that it is: (a) an adaptation of an established and efficacious intervention [2, 46, 47] now applied to post-9/11 Veterans; (b) nonstigmatizing (not “therapy” but a “skills workshop” to boost acceptance, adherence and retention); (c) transdiagnostic (open to all post-9/11 Veterans with self-reported reintegration difficulties; Veterans often have multiple mental health diagnoses, but it is not required for enrollment); (d) integrative (focus on the whole person rather than specific and often stigmatizing mental and physical health conditions); (e) comprised of Veteran-specific content to teach participants cognitive behavioral skills needed for successful reintegration (which led to greater acceptability in feasibility study); (f) targets anger and irritability, particularly during interactions with civilians; (g) emphasizes psychoeducation (including other available treatment options for common mental health conditions); and (h) challenges beliefs/barriers to mental health care to increase openness to future treatment and greater mental health treatment utilization. Many Veterans who participated in the development phases of this workshop have gone on to trauma or other focused therapies, or taken on vocational (work/school/volunteer) roles after STEP-Home.

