***Exclusion Criteria:*** Participants will be *excluded* for (1) schizophreniform disorder/active psychosis; (2) bipolar disorder; (3) active suicidality/homicidality requiring crisis intervention; (4) other severe psychiatric disorders prohibiting appropriate group participation; (5) neurological diagnosis prohibiting appropriate group participation (excluding TBI); (6) current substance dependence; (7) \*current participation in any other form of active behavioral therapy at the time of enrollment (e.g., Cognitive Processing Therapy, cognitive rehabilitation for mTBI, or other psychotherapy).

*\*For any potential participants who are currently participating actively in another treatment, they will be invited to participate in the next available cohort after their current treatment is complete.*

Enrolled STEP-Home participants will be instructed not to schedule initiation of another behavioral therapy until the 12-week intervention is complete. Importantly, Veterans will be allowed and encouraged to initiate any other treatment at the conclusion of STEP-Home or PCGT, even during the 12-week follow up. If another form of intervention is pursued during the actual 12-week intervention despite instruction to wait, we will allow participants to remain enrolled and track that information for use in statistical analyses similar to the 12-week post-intervention follow up period. We will, however, seek replacement participants for those who do this so that our statistical power is not diluted. Any necessary treatment for psychiatric crisis will also be allowed and tracked. Treatment enrollment and health utilization data will be collected at T1, T4, and T5 via self-report format and via CPRS chart review (please see Secondary Outcome Measures and Baseline Characteristics, protocol page 7). Psychotropic medication (and related visits) will be allowed if stable.

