Statistical Methods by Research Aims. The primary analysis for each aim will use an intent-to-treat (ITT) approach (i.e., all randomized subjects will be used in the analysis). ITT is optimal since it provides the least biased estimate of the treatment effect and the randomization balances STEP-Home and PCGT groups on known and unknown baseline confounders. This approach is appropriate for the proposed study given an anticipated low attrition rate of ~17% (based on attrition rates observed in our SPiRE study and Mt. Sinai's STEP RCT). We will implement quality assurance procedures to minimize protocol deviations and ensure correct treatment assignment according to the randomization. As a sensitivity analysis, we will conduct a per-protocol analysis in the subset of participants who complete an adequate amount of treatment ( $\geq 80\%$  of weekly sessions). We will assess the assumptions of homogeneity of variance and normality of residuals for each regression model and apply an appropriate transformation of the outcome if needed. We will address missing data, under the assumption of missing at random, using multiple imputation. Any subject characteristics associated with both the treatment group and primary outcome measure will be adjusted for in the final statistical model as specified in each aim.

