**Aim 2. Examine maintenance of treatment effects on primary outcomes:**

***Hypothesis 2: Treatment effects will be maintained at follow up in both groups.***

Differential treatment effect of STEP-Home over PCGT T4 will be maintained at T5

Statistical Methods: Mixed models, as described under Hypothesis 1B. We hypothesize that there will not be a significant interaction between group and time-point but the main effect of group will remain significant. Since subjects may initiate behavioral therapy post-intervention, we will conduct a secondary analysis to evaluate the impact of additional psychotherapy on the treatment effects. We will stratify by group and post-intervention therapy status (therapy/no therapy) and examine paired t-tests within each of the 4 strata.

**Exploratory Aim 1. Explore treatment effects of STEP-Home on measures of mental health, functional and vocational status and cognitive secondary outcomes targeted indirectly in the workshop.**

Statistical Methods: Paired t-tests and mixed models, as described in Primary Aims 1 and 2.

**Exploratory Aim 2. Acquisition of core skills (problem solving, emotional regulation, attention training) will mediate the effect of treatment on the primary outcomes post-intervention and follow up.**

Veterans demonstrating greater acquisition of core skills will evidence greater improvement in reintegration, readjustment, and anger post-intervention (T4) and at follow up (T5).

Statistical Methods: Exploratory mediation analyses will evaluate the potential causal pathway between treatment allocation and each primary outcome, with the core skills as mediators, using the SAS *mediation*

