macro developed by Valeri and VanderWeele [88]. We will run separate mediation analyses for each primary outcome and with each core skill (PS, ER, AT) as the mediator. We will evaluate acquisition of skills at two separate times during intervention (T2 and T3) as mediating the effect of treatment on post-intervention (T4). We will also examine skill acquisition at post-intervention (T4) as mediating the effect of treatment at follow up (T5). The mediation analysis will fit two models: (1) linear regression with the primary outcome as the dependent variable, group as the independent variable, and the mediator as a covariate and (2) linear regression with the mediator as the dependent variable and group as the independent variable. Both models adjust for any identified group-outcome and mediator-outcome confounders. The direct and indirect (mediating) effects are calculated from the beta coefficients of these two models and the 95% confidence intervals calculated using bootstrap (1000 replications). We will conduct a secondary analysis to evaluate the impact of any behavioral therapy initiated post-intervention for the post-intervention mediation analysis (i.e. core skills mediating effect T4 - T5), stratifying by post-intervention therapy status (therapy/no therapy).

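### The secondary Aim 2 analysis of additional psychotherapy never compares STEP-Home with PCGT, so it cannot answer its own question

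*Combined protocol and SAP*

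**What the plan says.** Under Aim 2 / Hypothesis 2 in the Analytic Plan, maintenance is tested with the mixed model of Hypothesis 1B: "We hypothesize that there will not be a significant interaction between group and time-point but the main effect of group will remain significant". Therapy status plays no part in that model, and "The primary analysis for each aim will use an intent-to-treat (ITT) approach".

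Because participants may begin behavioural therapy after the intervention, the plan adds: "we will conduct a secondary analysis to evaluate the impact of additional psychotherapy on the treatment effects". The method is to form four strata from randomised group and therapy status (yes/no) and to "examine paired t-tests within each of the 4 strata". The text does not name the paired time points. It gives no between-arm contrast, no interaction, no adjustment for the reasons Veterans start therapy, and no caution about causal reading.

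Therapy status is a matter of choice: "Veterans will be allowed and encouraged to initiate any other treatment at the conclusion of STEP-Home or PCGT" (section 4(c), exclusion criteria). Section 2(b) says STEP-Home challenges barriers to care "to increase openness to future treatment and greater mental health treatment utilization", and section 3 says the feasibility study showed more engagement with VA mental health care. Exploratory Aim 2 applies the same split by therapy status in a secondary version of its T4-to-T5 mediation analysis.

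**The concern.** The question concerns a difference between arms, because Aim 2 defines the effect to be maintained as the advantage of STEP-Home over PCGT. The method looks only at change within each stratum.

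Two further features make the four results easy to misread. First, therapy status arises after randomisation and may depend both on the arm and on how the Veteran is doing at T4, so the balance given by randomisation does not carry over to the strata. Secondly, strata of different size have different power, so a significant result in one and not in another may reflect size alone. At stake is a secondary claim that maintenance does, or does not, depend on further therapy.

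**Working it through.** **1. The plan's own figures.** Inputs from the Power Analysis: d = 0.44, one-sided 0.05, 80% power, attrition 20%, intraclass correlation 0.04. A cluster size of 8 comes from the target group size in section 4(b).
- Paired t-test: 33.33 per group; 2 × 33.33 / 0.8 = 83.3, which gives the stated 83.
- Between groups: 64.56, rounded up to 65 per arm; design effect 1 + (8 − 1) × 0.04 = 1.28; 130 × 1.28 / 0.8 = 208, as stated.

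No figure is given for the four-stratum analysis.

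**2. What is estimated.** Let D(g,s) be the mean change in group g and therapy status s. The four tests examine D(STEP-Home, yes), D(STEP-Home, no), D(PCGT, yes) and D(PCGT, no), each against zero. The stated question needs D(STEP-Home, s) − D(PCGT, s) for each s, and the difference between those two contrasts. None of the four tests gives either. This step needs no assumption.

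**3. Stratum size.** Completers: 208 × 0.8 ≈ 166, or 83 per arm (not the 83 of step 1, which is a total). Uptake is not in the documents, so 20% to 50% is assumed. Power of a paired t-test at d = 0.44, one-sided 0.05:

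| Uptake | Therapy n per arm | Power | No-therapy n per arm | Power |
|---|---|---|---|---|
| 20% | 17 | 53% | 67 | 97% |
| 30% | 25 | 69% | 58 | 95% |
| 50% | 42 | 87% | 42 | 87% |

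**4. Regression to the mean.** Simulation, 3,000 trials per scenario: 83 completers per arm, no true T4–T5 change, no effect of therapy, a constant 0.44 SD difference between arms, about 30% uptake, and two-sided tests at 0.05 of T4 against T5. The log-odds of starting therapy rise with the observed T4 score by the slope shown. Slope and correlation are assumptions; the ranges cover T4–T5 correlations from 0.8 to 0.5.

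| Slope per SD | Therapy: apparent improvement (SD) | Rejection | No therapy: apparent worsening (SD) | Rejection | At least one of 4 |
|---|---|---|---|---|---|
| 0 | 0.00 | 4–5% | 0.00 | 4–5% | 18% |
| 0.5 | 0.06–0.17 | 7.5–13% | 0.03–0.08 | 6–9% | 25–37% |
| 1.0 | 0.11–0.31 | 15–30% | 0.05–0.14 | 9–18% | 40–65% |

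At correlation 0.7 and slope 1.0, rejection is about 11% to 21%. If uptake instead follows the true, lasting score (slope 1.0, reliability 0.7), mean change is 0.00 in all four strata and rejection is 4.6% to 5.5%.

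**5. Does a between-arm contrast help?** At correlation 0.7 and slope 1.0, the mean changes are −0.165 (PCGT, therapy), +0.088 (PCGT, none), −0.189 (STEP-Home, therapy) and +0.065 (STEP-Home, none).
- Therapy minus none: PCGT −0.165 − 0.088 = −0.253; STEP-Home −0.189 − 0.065 = −0.254. The difference is about 0.00.
- STEP-Home minus PCGT: −0.024 with therapy, −0.023 without.

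The distortion largely cancels here because selection acts alike in both arms. It need not cancel if selection differs by arm.

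**6. Precision of the interaction.** At 30% uptake the strata are 24.96 and 58.24 per arm. In SDs of change, ignoring clustering, SE = √[2 × (1/24.96 + 1/58.24)] = 0.338. The smallest interaction detectable with 80% power is 0.338 × (1.645 + 0.842) = 0.84 one-sided, or 0.338 × (1.960 + 0.842) = 0.95 two-sided. With 240 × 0.8 = 192 completers it is 0.78 or 0.88.

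**7. Why not regress T5 on T4?** With a fully maintained difference of 0.44 SD and T4 reliability r, adjusting for T4 leaves a group coefficient of 0.44 × (1 − r): 0.13 at r = 0.7 and 0.18 at r = 0.6. Adding T1 at r = 0.7, with equally correlated scores, makes the T4 slope 0.7/1.7 = 0.412 and the coefficient 0.44 × 0.588 = 0.26. Neither is the maintained effect.

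**The case against.** The best defence is that this is labelled secondary. The maintenance estimate is an unstratified mixed model under intent-to-treat, the main mediation analysis is also unstratified, and nothing in the plan lets the strata override either. That stands, and it limits the point to a secondary analysis. The stratified mediation models also include group, so the missing-contrast criticism does not apply to them; only the conditioning on a post-randomisation variable does.

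A reader might infer that the four tests are bound to show spurious change. The documents do not support this. The paired time points are not named, although T4 against T5 is the natural reading: the Power Analysis describes paired tests of maintenance, and the parallel mediation analysis concerns T4 to T5. The Rationale links probable PTSD to more problems and more interest in services, but that describes lasting severity, which step 4 shows produces no inflation. Only a conditional *may* is justified.

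A reader might also infer that uptake will be higher after STEP-Home. That is possible, but the feasibility result is not a comparison with PCGT. PCGT covers the same gateway-to-care content, and starting therapy is encouraged in both arms.

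**Conclusion.** The point holds for the secondary analysis. Four within-stratum paired t-tests cannot show whether additional psychotherapy changes the effect of STEP-Home relative to PCGT. That conclusion follows from the text alone.

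The sizes rest on assumptions. Unequal strata give power of 69% against 95% at 30% uptake, but no gap at 50%. Regression to the mean is a risk only if T4 is paired with T5 and uptake follows the observed T4 score. At correlation 0.7, false rejection then ranges from about 5% to about 20% per stratum; the extreme assumed case (correlation 0.5, slope 1.0) reaches 30%. Uptake, correlation and slope are not in the documents, and the simulation assumes normal scores without clustering.

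A stronger inference, that the trial's maintenance conclusion is itself compromised, is not supported: the intent-to-treat model does not use the strata, and 83 and 208 both reproduce.

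**What to change.** - Keep the planned intent-to-treat mixed model as the maintenance estimate.
- Replace the four t-tests with one model across both arms that extends the planned mixed model. Use T4 and T5 as the time points, add therapy status with its lower-order interactions and the group × therapy × time term, and retain the planned clustering term.
- Report the STEP-Home minus PCGT contrast by therapy status, and the interaction, with confidence intervals. Report therapy uptake from T4 to T5 by arm.
- Label the analysis exploratory and non-randomised. A model of T5 adjusted for T4 may serve as a sensitivity check on the interaction, but its group coefficient must not be read as the maintained effect.
- State that the unstratified T4-to-T5 mediation is the main one and the therapy-stratified version is exploratory.

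The cost is SAP wording and one model per outcome. Treatment data are already collected at T1, T4 and T5 by self-report and chart review. The downside is low power: only an interaction of about 0.8 to 0.95 SD of change would be detected reliably at 30% uptake, so a null result should not be read as showing that therapy makes no difference.

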**Power Analysis.** Power calculations are made for the full study, including Phase 2 recruitment at site 2 (Houston). Power calculations were conducted on the primary aims (Aims 1 and 2) to observe an effect of Cohen's  $d=0.44$  or larger at one-tailed  $p<.05$  and  $\geq 80\%$  power. We selected a one-tailed p-value because all primary hypotheses were stated *a priori* as one-sided. We anticipated a small to medium effect size based on the Cohen's  $d=0.44$  observed in the subset of our SPiRE feasibility study ( $n=35$ ) who reported at least some difficulty on M2CQ, WHODAS, or Impulsive Aggression Scale (IAS). While we did not specifically collect pilot data on the PDRI or STAXI-2, we assume the effect size will be at least as strong as  $d=0.44$  observed on the proxy measures (WHODAS and IAS) since the PDRI and STAXI-2 are more sensitive and specific to post-9/11 Veterans. We further applied a conservative attrition rate of 20%, based on the attrition observed in our SPiRE feasibility study [1] and in Mt. Sinai's STEP RCT [2]. The univariate paired t-tests evaluating the improvement (Hypothesis 1A) and post-intervention maintenance (Hypothesis 2) of primary outcomes scores within the intervention groups required a total sample size of 83 after accounting for attrition. For Hypotheses 1B, the sample size was further adjusted to account for the clustering of subjects within the randomization cohort by applying an inflation of variance factor [71,89]. We used an interclass correlation of  $r=0.04$  as observed in a similarly designed group therapy RCT [65]. For the univariate post-intervention and change score analyses, we would need a total sample size of 208 after accounting for clustering and attrition. Thus, a total sample size of 208 is sufficient to power both primary aims.

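### The Aim 2 power statement rests on a within-arm paired t-test; 208 powers the between-arm difference at T5 only if d=0.44 persists, and no power is given for maintenance itself

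*Combined protocol and SAP*

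**What the plan says.** The Power Analysis gives two sample sizes. For Hypotheses 1A and 2 it relies on paired t-tests: "post-intervention maintenance (Hypothesis 2) of primary outcomes scores within the intervention groups required a total sample size of 83 after accounting for attrition". For Hypothesis 1B alone it adds a variance inflation for clustering ("We used an interclass correlation of $r=0.04$ as observed in a similarly designed group therapy RCT") and reaches 208. It then concludes: "Thus, a total sample size of 208 is sufficient to power both primary aims".

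In the Analytic Plan, Hypothesis 2 has a headline about effects lasting in both groups, followed by one operational line: "Differential treatment effect of STEP-Home over PCGT T4 will be maintained at T5". The method is given as "Statistical Methods: Mixed models, as described under Hypothesis 1B". The expected result is no significant group-by-time interaction, with the group main effect still significant. Under Aim 2, paired t-tests appear only in a secondary analysis within four strata of arm and post-intervention therapy status.

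**The concern.** The test that was sized is not the main test planned for Aim 2, and it does not address the between-arm quantity that Aim 2 claims. The sentence does not say which two time points the paired test compares.

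- **T4 against T5:** a test with 80% power for a 0.44 change is powered to detect a change after treatment. Failing to find one does not demonstrate maintenance.
- **T1 against T5:** the test shows whether an arm is still better than at baseline. It does not compare STEP-Home with PCGT.

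Maintenance is a primary aim, and the note on the 2023 extension at the head of the Analytic Plan gives adequate power for Aim 2 as a reason for raising enrolment. With the text as it stands, a non-significant interaction could be reported as adequately powered evidence that the advantage lasted. Attenuation is plausible: the section on exclusion criteria encourages participants in either arm to start other treatment during follow-up. The Power Analysis nevertheless gives no effect size or attrition specific to T5.

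**Working it through.** **Inputs from the plan.** d=0.44, one-sided 5%, power at least 80%, attrition 20% and ICC 0.04 (Power Analysis); equal arms and a target therapy group of 8 (Study Design). The Power Analysis does not state the cluster size; 8 is the value that reproduces its total.

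**Reproducing 83.** A paired t-test with 33 pairs has 79.6% power at d=0.44 (34 pairs: 80.7%). Two arms of 33: 66 / 0.8 = 82.5, rounded up to 83.

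**Reproducing 208.** A two-sample t-test needs 65 per arm. The design effect is 1 + 7 × 0.04 = 1.28. Then 130 × 1.28 / 0.8 = 208. Both totals follow from the plan's inputs, so the arithmetic is sound; the question is what the 83 is attached to.

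**Between-arm contrast at T5.** Effective n per arm is 208 × 0.8 / 2 / 1.28 = 65. The SE in SD units is √(2/65) = 0.1754. Power ≈ Φ(d₅/SE − 1.645), where d₅ is the T5 difference.

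- d₅ = 0.44: about 80% (exact t 80.2%, normal approximation 80.6%).
- d₅ = 0.33 (assumed): 59%.
- Group effect averaged over T4 and T5, with SE √((2/65)(1+ρ)/2) and d=0.44 at both: 89% at ρ=0.5, 84% at ρ=0.8.

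**At the current target.** The Study Design section can be read two ways.

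| Reading | Effective n per arm | T5 power at 0.44 |
|---|---|---|
| 240 randomised, 20% lost | 240 × 0.8 / 2 / 1.28 = 75 | 85% |
| 300 recruited, 240 complete | 240 / 2 / 1.28 = 93.75 | 91% |

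**The interaction test.** I take the Aim 2 model as comparing T4 with T5, since a null interaction would not be expected if T1 were included. ρ is the T4–T5 correlation, which the plan does not give. I assume a two-sided 5% test and carry the 1.28 over to this contrast. SE = √((2/65)(2 − 2ρ)). If the advantage falls from 0.44 to 0.22, the chance of a non-significant result is approximately Φ(1.96 − 0.22/SE).

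| ρ (assumed) | SE | Non-significant although half is lost |
|---|---|---|
| 0.5 | 0.1754 | 76% |
| 0.7 | 0.1359 | 63% |
| 0.8 | 0.1109 | 49% |

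**Illustration only: a direct test that half is kept.** Test D₅ − 0.5·D₄ > 0, where D₄ and D₅ are the between-arm differences at T4 and T5, and the truth is 0.44 at both. The mean is 0.22 and the SE is √((2/65)(1.25 − ρ)). One-sided 5% power at 208 is 42% at ρ=0.5 and 59% at ρ=0.8.

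**The case against.** The strongest reply is that 208 does serve much of Aim 2. One of the two parts of the planned criterion is a significant group effect. That part has about 80% power at T5 alone and 84% to 89% averaged over T4 and T5, if d=0.44 persists. The plan claims power only for effects of that size or larger, so the 0.33 scenario lies outside its claim. The headline of Hypothesis 2 also speaks of both groups, and a T1–T5 paired test bears on it directly: with 83 completers per arm and no clustering adjustment, its power at 0.44 is 99%. All of this stands. A reader might infer that 208 fails Aim 2 altogether, or that Hypothesis 2 has no place in the paired-test sentence; the documents support neither.

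A reader might also take the 42–59% as the trial's power for Aim 2. It is not. The plan contains no retention test, no retained share and no T4–T5 correlation, and the figure depends heavily on the share chosen. With share s, mean 0.44(1 − s) and SE √((2/65)(1 + s² − 2sρ)), requiring a quarter gives about 67% to 75%, and requiring three quarters gives 17% to 27%, over the same correlations.

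What the reply does not answer is that the between-arm calculation is offered for Hypothesis 1B only, that its extension to T5 is never stated or conditioned, and that the maintenance half of the criterion has no power figure.

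**Conclusion.** The concern holds in a limited form. The stated basis for Aim 2 power is a within-arm calculation that does not bear on the between-arm maintenance claim. The 208 does cover the Aim 2 group effect, on two conditions that the plan leaves unstated: d=0.44 is still present at T5, and no more than 20% are lost by T5. The maintenance part is unpowered as described. A non-significant interaction would occur about half to three quarters of the time even with half the advantage gone (49% to 76%).

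The T5 figures at d=0.44 use the plan's inputs with a group size of 8. The 0.33 difference, the halving of the effect, the correlations of 0.5 to 0.8, the two-sided interaction test and the use of one design effect for all contrasts are assumptions. The defect is a mismatch between test and claim; it does not show that the sample size was miscalculated.

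**What to change.** In the Power Analysis:

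1. Limit the paired t-test statement for Hypothesis 2 to within-arm improvement from T1 to T5.
2. Add the cluster-adjusted between-arm T5 calculation with an explicit T5 attrition assumption. Give it at 208 (80% at d=0.44) and at the current target, showing 240 both as randomised (85%) and as completers (91%).
3. Replace the closing sufficiency sentence. Say that 208 powers the Aim 2 group effect if d=0.44 persists at T5, that the trial is not powered to show that the T4 advantage is maintained, and that a non-significant interaction is not powered evidence of maintenance.

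Any retention calculation should be labelled as illustrative, with its share and correlations stated. The cost is a short calculation and revised wording, with no added participants or visits. The price is a less favourable description of Aim 2 power.

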**Aim 1. Examine treatment effects of STEP-Home on primary outcomes relative to PCGT:**

***Hypothesis 1A. Participants randomized into the STEP-Home intervention will show improvement on reintegration, readjustment, and anger post-intervention (expressed by lower scores; less difficulty).***

Military to Civilian Questionnaire (M2CQ), Post-Deployment Readjustment Inventory (PDRI), and State-Trait Anger Expression Inventory (STAXI-2) scores post-intervention (T4)  $<$  baseline (T1)

Statistical Methods: Paired t-tests will evaluate the difference between pre- (T1) and post-scores (T4), with a separate analysis for each primary outcome.

***Hypothesis 1B. Participants randomized into STEP-Home will show greater improvement in primary outcomes as compared to PCGT.***

1B.1: Change scores baseline (T1) to post-intervention (T4) STEP-Home  $>$  PCGT

1B.2: Post-intervention (T4) primary outcome scores STEP-Home  $<$  PCGT

Statistical Methods: Mixed models (PROC MIXED in SAS) will evaluate pre-post differences, with a separate model for each primary outcome. The Satterwaite option will be used to account for the clustering of subjects within cohorts (identified in Section 6.2) and calculate degrees of freedom accounting for any missing data. Group (STEP-Home/PCGT) will be the between-subjects factor and time-point (T1/T4) will be the within-subjects factor. We hypothesize that there will be a significant interaction between group and time-point, with a larger improvement between pre- (T1) and post-scores (T4) in STEP-Home than PCGT. While we do not anticipate a significant interaction by cohort or site, we will evaluate the 4-way interaction and all 2-way and 3-way interactions for time-point, group, cohort, and site. The model will be rerun removing any non-significant interactions. Linear regression will be used to evaluate the difference in post-intervention (T4) by group. The final mixed and regression models for each outcome will adjust for any identified confounders.

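### Hypothesis 1A's paired t-tests, and the sample size of 83 stated for the within-arm tests, ignore the therapy-group clustering that the plan allows for under Hypothesis 1B

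*Combined protocol and SAP*

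**What the plan says.** Under Aim 1, the statistical method for Hypothesis 1A is: "Paired t-tests will evaluate the difference between pre- (T1) and post-scores (T4), with a separate analysis for each primary outcome". No term for therapy group or cohort is mentioned. The mixed models for Hypothesis 1B, in the same section, are meant to account for clustering within cohorts. Exploratory Aim 1 reuses the unclustered test: "Paired t-tests and mixed models, as described in Primary Aims 1 and 2". Under Aim 2, the main analysis of Hypothesis 2 is the mixed model of Hypothesis 1B; paired t-tests appear only in a secondary analysis of four strata (arm by post-intervention therapy).

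The Power Analysis paragraph sets "one-tailed $p<.05$ and $\geq 80\%$ power" at d = 0.44 with 20% attrition. It says that the paired t-tests for Hypotheses 1A and 2 "of primary outcomes scores within the intervention groups required a total sample size of 83 after accounting for attrition". Only afterwards does it turn to clustering: "For Hypotheses 1B, the sample size was further adjusted to account for the clustering of subjects within the randomization cohort". There it takes an ICC of 0.04 from a similar group-therapy trial and arrives at 208 for both the post-intervention and the change-score analyses. Study Design (section 4(b)) gives a target of 8 Veterans per therapy group, a range of 4 to 10, and a current enrolment target of 240.

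**The concern.** The same Veterans, in the same groups and on the same outcomes, are treated as correlated for one primary hypothesis and as independent for another. In a between-arm comparison, a cohort effect common to both arms cancels. In a one-arm test of mean change nothing cancels, so all group-level variance enters the variance of the mean. If it is left out, the standard error is too small, the confidence intervals are too narrow and the test rejects too often. Hypothesis 1A is a stated primary hypothesis on three outcomes, so its error rate should be what the plan says it is. The sample size quoted for these tests should also deliver the power claimed for it.

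**Working it through.** **Inputs.** One-sided 5%, power of at least 80%, d = 0.44, attrition 20% and ICC 0.04 (Power Analysis). Therapy groups of 8, range 4 to 10 (Study Design). After 20% attrition, a group of 8 leaves 8 x 0.8 = 6.4 completers.

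**1. Reproducing the 83.** For a one-sample test on change scores, the noncentral t gives 79.6% power with 33 and 80.7% with 34. With 33 per arm, 2 x 33 / 0.8 = 82.5, so 83. With 34 per arm, 68 / 0.8 = 85. Neither contains a design effect.

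**2. Reproducing the 208.** The two-sample t-test needs 65 per arm, 130 in all. With design effect 1 + (8 - 1) x 0.04 = 1.28, 130 x 1.28 / 0.8 = 208.0. The plan does not print 1.28, but this reproduces its figure exactly.

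**3. Actual size of the paired t-test.** With design effect D = 1 + 0.04(m - 1) for m per group, the size is approximately P(Z > 1.645 / sqrt(D)).

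| m | D | Actual one-sided size |
|---|---|---|
| 4 | 1.12 | 6.0% |
| 6.4 | 1.216 | 6.8% |
| 8 | 1.28 | 7.3% |
| 10 | 1.36 | 7.9% |

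Simulation (40,000 replicates) agrees. With 33 completers per arm, the size was 6.2% in groups of about 4, 7.0% in groups of 6 to 7 and 7.5% in groups of 8 to 9. With 10 to 12 groups of 8 per arm it was still 7.4%, so more groups of the same size do not remove the excess. A t-test on group means held 4.9-5.2% throughout.

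**4. Power at 83 for a test held at a true 5%.** Completers per arm are 83 x 0.8 / 2 = 33.2.
- By effective sample size: 33.2 / 1.28 = 25.9 gives 70.4%, and 33.2 / 1.216 = 27.3 gives 72.4% (noncentral t; the normal approximation gives 72.4% and 74.4%).
- With group-level degrees of freedom there are only 4 to 5 groups per arm. Simulated power is 53% (groups of 8, 8, 8, 9) and 60% (groups of 7, 7, 7, 6, 6).

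**5. What the 83 becomes.**
- By the plan's design-effect method: 66 x 1.216 / 0.8 = 100.3, so 101; 66 x 1.28 / 0.8 = 105.6, so 106; 68 x 1.28 / 0.8 = 108.8, so 109.
- With group-level degrees of freedom (noncentral t, df = groups - 1), in whole groups per arm: 7 groups of 6.4 completers (2 x 44.8 / 0.8 = 112 enrolled) give 76%, and 8 groups (2 x 51.2 / 0.8 = 128) give 82%. Six groups of 8 completers (2 x 48 / 0.8 = 120) give 75%, and 7 groups (2 x 56 / 0.8 = 140) give 82%.

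**6. Power at the planned enrolment.** With D = 1.28, corrected power at 208 is 97% by effective sample size and 95% with group-level degrees of freedom. At 240 it is 98% and 97%. With groups of 10 throughout, the group-level figures fall to 93% and 96%.

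**The case against.** Five arguments can be made for leaving the text alone.

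- **No decision rests on the 83.** The trial is sized at 208 and now targets 240. This stands. A reader might infer that the trial is underpowered for Hypothesis 1A, but step 6 shows that it is not.
- **The ICC is borrowed.** It comes from another trial and is described as clustering within the randomization cohort, which holds both arms. Its value for one-arm change is an assumption. However, the plan makes the same assumption for change scores under Hypothesis 1B, and within one arm each cohort supplies exactly one therapy group.
- **Groups may be smaller than 8.** If 240 Veterans are spread over 20 cohorts (an assumption), each group starts with 6 and keeps 4.8. The size is then 6.3%, power at 83 about 74%, and the design-effect figure about 95-98. The effect shrinks but does not vanish.
- **Hypothesis 2 is mostly untouched.** Its main analysis is a mixed model intended to allow for clustering. A reader might take the paired-test sizing in the Power Analysis to mean that Hypothesis 2 shares the inflated error rate. The Aim 2 text does not support that: the point reaches only its stratified secondary t-tests. What remains is a mismatch between the two places.
- **The excess is small beside other limits of an uncontrolled comparison.** Veterans enter because they report difficulty, so regression to the mean alone could produce improvement. That is fair, and the efficacy claim rests on Hypothesis 1B. It does not justify a miscalibrated test of a primary hypothesis when the remedy is nearly free.

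It would also be wrong to read the 6-8% size and the 70-72% power as properties of one test. The planned unadjusted t-test has about 78% power at 83, but only at its inflated error rate. The lower figures belong to a test held at a true 5%.

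**Conclusion.** The point holds for Hypothesis 1A and for the stated 83. At an ICC of 0.04, the planned paired t-test has a true one-sided size of about 6.0% to 7.9% over group sizes of 4 to 10, and about 7% near the target size. More Veterans in groups of the same size will not correct it. The 83 does not provide 80% power once clustering is allowed for: about 70-72% by effective sample size and about 50-60% with group-level degrees of freedom. Both results assume that the plan's ICC applies to within-arm change and that groups are near the planned size. The documents do not support a claim that enrolment is too small, or that the main analysis of Hypothesis 2 has this error.

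**What to change.** 1. For Hypothesis 1A, replace the paired t-test with an intercept-only mixed model of the T1-T4 change score with a random therapy-group effect (Satterthwaite or Kenward-Roger degrees of freedom), or with a t-test on therapy-group mean changes. State in advance which one is used.
2. Do the same for the paired tests reused in Exploratory Aim 1 and in the stratified secondary analysis of Hypothesis 2.
3. In the Power Analysis, restate the 83 and name the method. By the plan's own design-effect approach it is about 101-109 (106 with its 33 per arm and 1.28). For 80% power with group-level degrees of freedom and 6.4 to 8 completers per group, it is about 128-140. The 109 should not be paired with a group-level test, because it falls short of 80% there.
4. Reconcile the Power Analysis, which sizes Hypothesis 2 by paired t-tests, with Aim 2, which names mixed models as its main analysis.

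The cost is a few lines of analysis text, slightly wider intervals and one less favourable stated figure. No additional participants are needed.
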